### 21.3.4 Variables Related to Times and Durations

#### Convention

Time calculated in days will be converted in months using the convention:

$$1 \text{ month} = 365.25 \div 12 \text{ days} = 30.4375 \text{ days}$$

#### Study duration

The study duration will be derived in months as:

$$(\text{Date of the last follow-up visit} - \text{Date of the first Ozurdex injection in the study eye} + 1) \div (365.25 \div 12). \text{ The result will be rounded to 0.1.}$$

#### Age at baseline

Age of patient at baseline will be derived in years as:

$$\text{Year of the first Ozurdex injection in the study eye} - \text{Year of birth.}$$

#### Time to baseline

For a given event E, the time from the event E to baseline will be derived in months as:

$$(\text{Date of the first Ozurdex injection in the study eye} - \text{Date of Event E}) \div (365.25 \div 12). \text{ The result will be rounded to 0.1.}$$

This derivation rule will be applied for the following times calculated in months: time from DME diagnosis to baseline, time from onset of DME symptoms to baseline, time from onset of glaucoma to baseline, time from onset of ocular hypertension to baseline, time from the last retinal laser treatment to baseline, time from the last retinal surgery to baseline, time from the last anti-VEGF/Corticosteroid treatment to baseline.

The time from diabetes diagnosis to baseline will be derived in years as:

$$(\text{Date of the first Ozurdex injection in the study eye} - \text{Date of diabetes diagnosis}) \div 365.25. \text{ The result will be rounded to 0.1.}$$

### Duration of AESI

The duration will be derived in days as: End date of AESI – Onset date of AESI +1.

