#### **10.9.2 Collection and reporting of Safety Events by Investigators**

The study will be conducted in accordance with Directive 2001/83/EC, Regulation (EC) No 726/2004, Commission Implementing Regulation (EU) No 520/2012 as amended and detailed in GVP Modules VI.

Considering that study aims to explore the potential impact of recurrent Ozurdex injections, and not confirm the whole safety profile, and considering the current knowledge of the study drug safety profile, this study focuses only on the following AESIs (related or not to Ozurdex):

- **Glaucoma**, defined as damage to the optic nerve with progressive vision loss (open angle glaucoma, normal tension glaucoma, and acute angle closure glaucoma)
- **Intraocular hypertension**, defined as IOP without meeting the criteria for glaucoma
- **Hypotony**, defined as low IOP  $\leq 5$  mmHg
- **Cataract or lens opacities** (nuclear sclerotic, cortical and posterior subcapsular)
- **Ocular bleeding or hemorrhage** (conjunctival, anterior chamber, vitreous, macular, retinal)
- **Retinal detachment, tear or hole**
- **Vitreous detachment**
- **Infection vs. Non-infection related Ocular inflammation** (conjunctivitis, blepharitis, episcleritis, scleritis, keratitis, uveitis, retinitis and endophthalmitis)
- **Significant vitreous loss**
- **Mechanical failure of device and implant misplacement**
- **Implant dislocation**

In addition to AESIs, off-label use should be collected, and reported to Allergan whether or not off-label use was associated with an AE.

Due to the retrospective design of the study, the reporting of safety events to the sponsor is not solicited for this study. However, investigators are reminded about the possibility for them to report

any suspected ADRs directly to the marketing authorization holder of the suspected medicinal product (studied or not) or to the concerned competent authority via the national spontaneous reporting system.

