## **7.0 BIAS AND LIMITATIONS**

Selection bias is a potential limitation of the study, for both sites and patients. Sites will be selected from hospital-based experienced medical retina centers treating DME patients, as these centers will be experienced in intravitreal Ozurdex injections. Because the participating sites comprise a population of volunteers, non-response bias is possible.

In order to limit bias in the selection of patients, sites will attempt to consecutively select all patients who meet the selection criteria, regardless of demography or other considerations, based on the date of first Ozurdex implant injection. All patients meeting the selection criteria, regardless of their selection for the study, will be identifiable in a screening log collecting minimum non-identifying patient information (see Section 6.1). Characteristics of selected and non-selected patients will be compared to assess patient selection bias and reason for not being selected will be described (patient did not meet selection criteria, lack of time, quotes were met, etc.).

Information bias is a distortion in the estimate of association between risk factor and disease due to systematic measurement error or misclassification of patients on one or more variables, either risk factor or disease status. As the study is retrospective, it relies on data that have already been collected for another purpose (i.e. patient care). As a result, not all data to be collected in this study may be recorded in the medical charts, leading to a potential bias due to missing data. Moreover, as the study is anonymous, no queries will be issued to the sites in case of missing or incoherent data. Finally, as this is a multicenter study, the methods used to estimate the variables collected during the chart review process may be heterogeneous across sites. This has the potential to introduce systematic bias into the results.

Information bias is minimized by the use of EDC technology. In addition, to minimize the burden on investigators and sites, the EDC will maximize the quality and relevance of the data using automated online controls. To complement these automated online controls, principal investigators will be requested to review all entered data submitted in the EDC.

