### 15.2.4 Fourth Secondary Objective

The secondary objective '*To present those AESIs that may be potentially related to Ozurdex reinjection*' will be assessed by the presence of the following AESIs:

- Cataract or lens opacities
- Glaucoma
- Hypotony
- Implant dislocation
- Infection vs. Non-infection related ocular inflammation
- Intraocular hypertension
- Mechanical failure of device and implant misplacement
- Ocular bleeding or hemorrhage
- Retinal detachment (tear or hole)
- Significant vitreous loss
- Vitreous detachment

These AESIs will be identified from eCRF section '*Adverse events*' (AE/F20 form) in which they are pre-listed.

All AESIs that began on or after the date of the first Ozurdex injection in the study eye will be considered for analysis. The analysis will be performed:

- considering all AESIs, AESIs that occur in the study eye, and AESIs that occur in the contralateral eye.
- cumulatively considering all AESIs and broken down by the number of injections, i.e. considering AESIs that occur after the first Ozurdex injection at baseline, AESIs that occur after the first Ozurdex reinjection, AESIs that occur after the second Ozurdex reinjection, etc. AESIs that occur on the same day of an Ozurdex injection will be considered as occurring after the injection.

AESIs will be summarized using descriptive statistics for the following parameters:

- Number and percentage (with 95% CI) of patients who experienced at least one AESI.

[REDACTED]

[REDACTED]

[REDACTED]

[REDACTED]

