## **21.0 DATA HANDLING CONVENTIONS**

### **21.1 STATISTICAL RULES AND DATA FORMATS**

#### Continuous variables

Continuous (quantitative) variables will be described by the number of non-missing and missing observations, mean, SD, median, first and third quartiles and extreme values (minimum and maximum). The following rules will be applied:

- If the raw/derived variable is an integer, then mean, median, SD, first and third quartiles will be rounded to one decimal.
- If the raw/derived variable is a decimal number, then mean, median, SD, first and third quartiles will be reported using the same number of decimal places as the raw/derived data.
- Minimums and maximums will be reported with the same number of decimals with which the raw/derived variable is recorded/calculated.
- If the standard deviation is not computable, then it will be displayed as 'NA' (Not applicable).

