### **21.4 IMPUTATION OF MISSING DATA**

Partial date fields with missing day will be imputed as the first of the month. Partial date fields with missing day and month will be imputed as 01JUL.

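### AESI duration has no rule for events that have not ended, and an imputed end date can fall before onset; both gaps affect a minor descriptive safety variable

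*SAP*

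**What the plan says.** The complete derivation in SAP 21.3.4 (Duration of AESI) is "End date of AESI – Onset date of AESI +1", in days. It has no branch for an absent end date.

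SAP 21.4 has two imputation rules: "Partial date fields with missing day will be imputed as the first of the month" and "Partial date fields with missing day and month will be imputed as 01JUL". Neither separates onset from end dates or compares the imputed date with any other date. Both cover partial dates, so a wholly absent end date stays absent.

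SAP 15.2.4 sets the scope of the safety analysis: "All AESIs that began on or after the date of the first Ozurdex injection in the study eye will be considered for analysis". Resolution is not required. The one AESI summary that can be read there is "Number and percentage (with 95% CI) of patients who experienced at least one AESI"; the items after it are redacted. SAP 21.1 applies to any continuous variable: "Continuous (quantitative) variables will be described by the number of non-missing and missing observations", followed by the usual summary statistics.

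The AESI list in Protocol 10.9.2 includes cataract or lens opacities and glaucoma, the latter "defined as damage to the optic nerve with progressive vision loss". Data stop at 1 September 2018. SAP 7.0 adds that "no queries will be issued to the sites in case of missing or incoherent data".

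**The concern.** Two separate gaps meet in one derived variable.

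The first is selection. Duration exists only for AESIs that ended before the chart was closed. The events most likely to be open at that point are the lasting ones, and glaucoma and cataract are on the list. A mean or median over ended events would understate how long such AESIs persist.

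The second is arithmetic. If an end date lacks its day and the onset date is complete, the end can be moved to before the onset, giving a duration of zero or less. Sites cannot be queried, so the analysis rule has to deal with it.

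At stake is whether a reader of the safety tables can tell brief events around the injection from lasting ones, and whether the tables contain impossible values.

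**Working it through.** The documents state no AESI duration, so there is no planned figure to reproduce. The inputs are the formula in SAP 21.3.4, the two rules in SAP 21.4, and the follow-up limits: at least 12 months, and at most 44 months (1 January 2015 to 1 September 2018).

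**1. Partial dates, single cases**

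- Onset 20 March, end known only as March of the same year: 1 - 20 + 1 = -18 days.
- Onset 25 March, true end 7 April (14 days), end known only as April: 1 April minus 25 March is 7 days, plus 1 gives 8 days.
- Lowest value when only the end day is missing: onset on the 31st, 1 - 31 + 1 = -29 days.
- End known only by year (01JUL), non-leap year: onset 31 December of that year gives -182 days; onset 1 January gives +182 days.

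**2. Partial dates, every onset day from 2015 to 2017**

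The mean error is derived minus true duration.

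| What is missing | Mean error (days) | Can be zero or negative? |
|---|---|---|
| End day only | -14.7 | Yes |
| Onset day only | +14.7 | No |
| Both days | 0.0 | No (minimum 1) |
| End day and month only | -0.8 | Yes |

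With only the end day missing, the result is zero or below when the event starts on day 2 or later and ends in the same month. For a true duration of D days in a month of L days, that share is (L - D)/L. With an average L of 30.44:

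- D = 7: (30.44 - 7)/30.44 = 77%
- D = 14: (30.44 - 14)/30.44 = 54%
- D = 21: (30.44 - 21)/30.44 = 31%

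The full enumeration agrees. It gives 1.9% at 30 days and none at 60 days or more. With an end known only by year, the share is 48% at 7 days, 26% at 90 days and 1% at 180 days.

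**3. Ongoing AESIs**

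The documents give no AESI durations, so this part is a simulation under assumptions: follow-up uniform over 12 to 44 months, onset uniform within follow-up, exponential duration, one million events per row. The shortfall is 1 minus resolved-only mean divided by true mean.

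| True mean (days) | Ongoing | Resolved-only mean (days) | Shortfall |
|---|---|---|---|
| 14 | 1.8% | 13.7 | 2% |
| 30 | 4.0% | 28.8 | 4% |
| 90 | 12.0% | 78.0 | 13% |
| 180 | 23.2% | 131.3 | 27% |
| 365 | 40.7% | 193.4 | 47% |
| 730 | 60.0% | 244.0 | 67% |

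Using the last visit as the end date does not cure this: at a true mean of 365 days it gives 216 days.

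**The case against.** The strongest reply is that no visible analysis uses duration. The AESI parameters after the first in SAP 15.2.4 are redacted, as is the matching text in Protocol 14.2.2.3.4. Those lines may report outcome or number ongoing, or restrict duration to resolved events. The visible safety outcome in Protocol 6.2 is the number and percentage of patients with AESIs, which duration does not touch. This stands, and it limits the weight of the point. It does not supply the missing rule in SAP 21.3.4, which can be read in full.

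A reader might infer that ongoing AESIs drop out of the safety analysis. The documents do not support that. SAP 15.2.4 counts every AESI from the first injection onward, and SAP 21.1 would show absent durations in the missing count. That count cannot, however, separate an event still present from one whose end was not charted.

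A reader might also infer that the first-of-month rule makes AESIs look shorter throughout. It does so only when the end day alone is missing. The error reverses when the onset day alone is missing and averages zero when both are.

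The plan also has online logic checks at entry (Protocol 12) and an outlier review before database lock (SAP 21.5). These may reduce the number of bad values, but a negative duration created by imputation arises after entry and still needs a stated rule.

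**Conclusion.** The point holds as a minor one about a descriptive safety variable. As written, the derivation gives no duration to an AESI that has not ended, so any duration summary covers resolved events only. For events lasting weeks the shortfall is a few per cent at most. For events with a true mean of one to two years it is about 47% to 67%, under the assumed exponential durations and uniform onset and follow-up.

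Impossible values are conditional. They need a partial end date and a more complete onset date in the same month, or in the same year under the 01JUL rule. Where the end day alone is missing, 77% of 7-day and 54% of 14-day events come out at zero or below.

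The documents do not say how many AESI dates are partial or how many AESIs are ongoing, so the total effect cannot be sized. AESI incidence and the primary objective are unaffected.

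**What to change.** **SAP 21.4.** Add that an imputed AESI end date may not fall before the onset date or after the last study visit. Otherwise keep the existing rules. With the floor at onset, the smallest possible duration is 1 day. Do not move end dates to month-end or 31 December: the first changes the mean error from 0.0 to +29.5 days when both days are missing, and the second changes it from -0.8 to +182.2 days when the end day and month are missing (both before any cap at the last visit).

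**SAP 21.3.4.** Flag an AESI that has not ended by the last study visit as ongoing. For each AESI term, report the number and percentage ongoing, separately from those whose end date was not recorded, and label the duration as covering resolved AESIs only. The split depends on what the adverse event form records, which the documents do not show. If it cannot be made, report a single row for AESIs without an end date and say so.

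A Kaplan-Meier median censored at the last study visit is optional. If it is used, name that date explicitly, because SAP 21.2 also ends follow-up at the first concomitant anti-VEGF or corticosteroid treatment. The median may not be reached for lasting AESIs.

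**Cost.** A few lines of SAP text, slightly more programming and one more table row.

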### Time from the last Ozurdex injection (before or the day of AESI) to AESI

The time will be derived in days as:

Onset date of AESI – Date of the last Ozurdex injection. The last Ozurdex injection will be identified as the last injection among those performed on or before the onset date of the AESI.

### **21.3.5 Variables Related to BCVA and CRT**

#### BCVA conversion

The method of assessment for BCVA can be reported in the EDC as ETDRS, Snellen (Feet), Snellen (Meters), or Snellen (Decimal). For analysis, all values will be converted into approximate ETDRS letters.

Snellen converted to approximate ETDRS letters =  $85 + [50 * \log(\text{Snellen fraction})]$

BCVA and CRT: Last assessment prior to each Ozurdex injection

For the first Ozurdex injection in the study eye, the last assessment prior to Ozurdex injection (= baseline assessment) is specifically requested in the eCRF. Therefore, the last assessment is directly available.

For subsequent Ozurdex injections in the study eye, the last assessment prior to the  $j^{\text{th}}$  injection ( $j \geq 2$ ) will be identified considering all assessments available between the day after the  $(j-1)^{\text{th}}$  injection to the day of the  $j^{\text{th}}$  injection included (i.e. date of  $(j-1)^{\text{th}}$  injection  $<$  Date of assessment  $\leq$  Date of  $j^{\text{th}}$  injection). The underlying assumption is that assessments performed at a visit at which an Ozurdex injection is performed are considered as performed before the injection.

BCVA and CRT: Change from baseline to 7-12 weeks following injection  $j$

For each injection  $j$  ( $j \geq 2$ ), the change will be calculated as:

Value at 7-12 weeks following injection  $j$  – Last value prior to the first (baseline) Ozurdex injection in the study eye. See Section 21.2 for the definition of the '7-12 weeks' time window and for the rule in case of multiple assessments within the time window.

BCVA and CRT: Change from the assessment prior to injection  $j$  to 7-12 weeks following injection  $j$

For each injection  $j$  ( $j \geq 1$ ), the change will be calculated as:

Value at 7-12 weeks following injection  $j$  – Last value prior to Ozurdex injection  $j$ . See Section 21.2 for the definition of the '7-12 weeks' time window and for the rule in case of multiple assessments within the time window.

### **21.3.6 Other Variables Derived From Data Entered in eCRF**

Eye with history of steroid response

The variable will be defined from the side of the study eye (OS/OD, eCRF section '*Demographics and DME history*' (DM/F2 form)) and from the variable '*1.3.1. – Specify eye(s)*' (eCRF section '*Ophthalmic history (prior to first Ozurdex injection in Study eye)*' (OH/F4 form)). The variable will be derived to:

- Study eye, if the variable '*I.3.1. – Specify eye(s)*' is equal to the side of the study eye
- Contralateral eye, if the variable '*I.3.1. – Specify eye(s)*' is equal to the side of the contralateral eye
- Both eyes, if the variable '*I.3.1. – Specify eye(s)*' is equal to 'OU (Both)'

**Eye with glaucoma, Eye with ocular hypertension**

These two variables will be derived in the same way that the variable 'Eye with history of steroid response' (See above).

**At least one adverse finding in study eye at biomicroscopy (Yes, No)**

Using information from eCRF section '*Biomicroscopy in study eye*' (BIO/F9 form) the variable will be derived to:

- Yes, if the variable '*I.1.2. - Any adverse finding?*' is equal to 'Yes' at baseline or at least once at a follow-up visit
- No, if the variable '*I.1.2. - Any adverse finding?*' is equal to 'No' at baseline or at all follow-up visits of the patient
- Missing, if the variable '*I.1.2. - Any adverse finding?*' is missing at baseline or at least once at a follow-up visit and is not equal to 'Yes' at the other follow-up visits.

Biomicroscopy in the study eye: adverse finding categorized as 'Present' vs. 'Absent'

For hyperemia, edema (in conjunctiva and cornea), subconjunctival hemorrhage, superficial punctate keratopathy, adverse finding will be considered:

- Absent, if the result is 'Normal'
- Present, if the result is 'Trace +0.5', 'Mild +1', 'Moderate +2' or 'Severe +3'

For cells, adverse finding will be considered:

- Absent, if the result is 'Normal'
- Present, if the result is '+0.5', '+1', '+2', '+3' or '+4'

For flare, adverse finding will be considered:

- Absent, if the result is 'Normal'
- Present, if the result is 'Faint +1', 'Moderate +2', 'Marked +3' or 'Intense +4'

For rubeosis iridis, adverse finding will be considered:

- Absent, if the result is 'Normal'
- Present, if the result is '+0.5', '+1', '+2' or '+3'

At least one adverse finding in study eye at ophthalmoscopic examination (Yes, No)

The variable will be derived in the same way that the variable 'At least one adverse finding in study eye at biomicroscopy during the follow-up period' (See definition above) using information from eCRF section '*Ophthalmoscopic examination in the study eye*' (OE/F10 form).

Ophthalmoscopic examination in the study eye: adverse finding categorized as 'Present' vs. 'Absent'

For cells, haze and hemorrhage in vitreous, adverse finding will be considered:

- Absent, if the result is 'Normal'
- Present, if the result is '+0.5', '+1', '+2', '+3' or '+4'

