### **12.2 BIOMICROSCOPY**

At baseline, the number and percentage of patients with biomicroscopy data available for the study eye will be described. Then, for patients with data available, the following parameters will be described:

- Any adverse findings (Yes, No)
- Conjunctiva (bulbar or palpebral): hyperemia (Normal, Trace +0.5, Mild +1, Moderate +2, Severe +3), edema (Normal, Trace +0.5, Mild +1, Moderate +2, Severe +3), subconjunctival hemorrhage (Normal, Trace +0.5, Mild +1, Moderate +2, Severe +3). Adverse findings will also be described as 'Absent vs. Present' [DV].
- Cornea: edema (Normal, Trace +0.5, Mild +1, Moderate +2, Severe +3), superficial punctate keratopathy (Normal, Trace +0.5, Mild +1, Moderate +2, Severe +3). Adverse findings will also be described as 'Absent vs. Present' [DV].

- Anterior chamber: cells (Normal, +0.5, +1, +2, +3, +4), flare (Normal, Faint +1, Moderate +2, Marked +3, Intense +4), hypopyon (Present, Absent) and, if present, level in mm. Findings on cells and flare will also be described as 'Absent vs. Present' [DV].
- Iris/Pupil: pathology (Present, Absent), peripheral iridotomy noted (Yes, No), rubeosis iridis (according to categories 'Normal, +0.5, +1, +2, +3'). Adverse findings will also be described as 'Absent vs. Present' [DV]. Pathologies will be described by PT (MedDRA version 21.1). If more than one pathology with the same PT have been reported for the same patient, s/he will be counted once for that PT.

During the follow-up period, the number and percentage of patients having at least one adverse finding in the study eye (Yes, No) [DV] will be described. Then, for all patients with at least one adverse finding, the type of adverse finding will be described as 'Present, absent' for each pre-listed category: conjunctiva (hyperemia, Edema, subconjunctival hemorrhage), cornea (edema, superficial punctate keratopathy), anterior chamber (cells, flare, hypopyon) and iris/pupil (pathology, peripheral iridotomy, rubeosis iridis). If an adverse finding has been reported more than once for the same category for the same patient, s/he will be counted once for that category. For patients with at least one adverse finding during the follow-up period, a listing will also be presented with all biomicroscopy results at baseline and during the follow-up period.

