### Follow-up period

The period starting the day after the day of the first Ozurdex injection in the study eye is the follow-up period (= post-baseline period). End of follow-up occurs at the last study visit or first receipt of concomitant treatment with anti-VEGF and/or corticosteroids, whichever comes first.

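### As written, the adverse-finding flag reported for follow-up takes in baseline, and its Yes, No and Missing rules overlap with no stated precedence

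*SAP*

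**What the plan says.** SAP 12.2 (biomicroscopy) and 12.3 (ophthalmoscopy) treat baseline and follow-up separately. At baseline, whether there was any adverse finding is summarized as collected, with no derived-variable tag. For the follow-up period, "the number and percentage of patients having at least one adverse finding in the study eye (Yes, No) [DV] will be described". The same flag then selects the patients whose findings are broken down by type. A listing of baseline and follow-up results is also given for patients with a follow-up finding.

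SAP 21.2 defines the period: "The period starting the day after the day of the first Ozurdex injection in the study eye is the follow-up period". Baseline therefore lies outside it.

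SAP 21.3.6 gives the only derivation of the flag. The eCRF item on adverse findings leads to:

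- Yes, if it "is equal to 'Yes' at baseline or at least once at a follow-up visit";
- No, if it "is equal to 'No' at baseline or at all follow-up visits of the patient";
- Missing, if it "is missing at baseline or at least once at a follow-up visit and is not equal to 'Yes' at the other follow-up visits".

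The heading of that derivation names no period. When the rule is carried over to ophthalmoscopy, the same section calls the variable "At least one adverse finding in study eye at biomicroscopy during the follow-up period".

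**The concern.** The flag is reported as a follow-up result, but its rule lets a baseline finding alone produce Yes. The Yes and No conditions are also each joined by 'or' across the two periods, so one patient can satisfy both, and the SAP does not say which wins. Two programmers could each follow the text faithfully and report different percentages.

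What is at stake is the follow-up percentage in two descriptive examination tables, the by-type tables restricted to flagged patients, and possibly who appears in the accompanying listings.

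**Working it through.** **Inputs.** The three conditions in SAP 21.3.6; the reporting items in SAP 12.2 and 12.3; the start of follow-up in SAP 21.2. The plan gives no figure to reproduce.

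**Step 1: apply the conditions literally.** Baseline status can be Yes, No or Missing. Follow-up status can be at least one Yes, all No, or at least one missing with no Yes. That makes 9 combinations.

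| Baseline | Follow-up visits | Conditions met in 21.3.6 | Follow-up-only rule |
|---|---|---|---|
| Yes | at least one Yes | Yes | Yes |
| Yes | all No | Yes and No | No |
| Yes | missing, no Yes | Yes and Missing | Missing |
| No | at least one Yes | Yes and No | Yes |
| No | all No | No | No |
| No | missing, no Yes | No and Missing | Missing |
| Missing | at least one Yes | Yes | Yes |
| Missing | all No | No and Missing | No |
| Missing | missing, no Yes | Missing | Missing |

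Four combinations get one value. Two meet both Yes and No, and three collide with Missing. A rule using follow-up visits only gives exactly one value in all nine.

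**Step 2: direction of the error.** Suppose no data are missing. Let b be the share with a baseline finding, f the share with a finding at one or more follow-up visits, and c the share with both.

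- Follow-up-only flag: f.
- Literal rule, Yes first: b + f − c, an excess of b − c (patients whose only finding was at baseline).
- Literal rule, No first: c, a shortfall of f − c (patients with a finding only after a clean baseline).

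**Step 3: illustration.** The documents give none of b, f or c. Assume b = 20%, f = 10% and the planned N = 150. The follow-up-only flag gives 0.10 × 150 = 15 patients (10%).

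| Overlap c | Yes first: b + f − c | No first: c |
|---|---|---|
| 0% (none in common) | 20 + 10 − 0 = 30% | 0% |
| 2% (independent: 0.20 × 0.10) | 20 + 10 − 2 = 28%, or 42 patients | 2%, or 3 patients |
| 10% (all follow-up findings in patients with one at baseline) | 20 + 10 − 10 = 20% | 10% |

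Under independence, (20 − 2) + (10 − 2) = 26% of patients qualify as both Yes and No.

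The excess under Yes first disappears if every baseline finding persists to a follow-up visit. Then c = b and the literal rule gives b + f − b = f. The size of the error therefore turns on persistence, which is unknown.

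**Step 4: knock-on.** In the independent case with Yes first, the by-type tables would describe 42 patients instead of 15. The extra 27 would show every follow-up finding as absent, which dilutes each type's percentage.

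**The case against.** The strongest reply is that the rule was meant to be read period by period: the baseline clause for a baseline flag and the follow-up clause for a follow-up flag. The No condition makes sense only that way. The section's own later name for the variable mentions only follow-up, and 12.2 and 12.3 keep the periods apart. This reading is plausible and would remove the overlap between Yes and No. It does not clear the text. SAP 21.3.6 defines one variable and does not say that the clauses apply separately. The baseline item carries no derived-variable tag, so it needs no derivation.

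The reply is right about stakes. Baseline findings are tabulated separately, and the listings show baseline next to follow-up results, so a careful reader could spot pre-existing findings. The adverse events of special interest come from the adverse events form (SAP 15.2.4) and do not use this flag.

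A reader might go further and infer that the percentage will certainly be inflated, or that for ophthalmoscopy it will be close to 100% because these patients have macular edema at baseline. The documents support neither inference. The direction depends on a precedence that is not stated. The flag rests on one eCRF question, and nothing says whether sites answer Yes for the underlying edema. If they do, edema still recorded at follow-up visits could push a follow-up-only flag just as high.

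**Conclusion.** The point holds as a faulty stated rule of limited consequence. Read literally, SAP 21.3.6 takes baseline into a follow-up percentage and leaves 5 of 9 status combinations with two values. The percentage is too high where Yes takes precedence and some baseline findings do not persist. It is too low where No takes precedence and some patients have a new adverse finding after a clean baseline.

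The amount cannot be stated from the documents. The 0% to 30% spread against a correct 10% in the illustration rests on assumed prevalences and no missing data. The fault carries into the ophthalmoscopy flag and the by-type tables. The listings are exposed too if they are built on the flag. The primary objective and the analysis of adverse events of special interest are untouched.

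**What to change.** Rewrite the three conditions in SAP 21.3.6 to use follow-up visits only:

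- Yes, if Yes at one or more follow-up visits;
- No, if No at all follow-up visits;
- Missing, if at least one follow-up visit is missing and none is Yes.

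This is the pattern that SAP 21.3.3 already uses for change in lens status. It keeps the present principle that an unrecorded follow-up visit without any Yes gives Missing, not No. State the period in the heading, and confirm that the ophthalmoscopy flag follows the same rule. Leave the baseline item as a separate summary, as 12.2 and 12.3 already have it.

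A follow-up-only flag still counts findings that persist from baseline. If the team wants new findings, it can add an optional flag for findings absent at baseline and present in follow-up. A 'worsened' version is possible only for graded items. In the ophthalmoscopic examination, macular edema, hemorrhage and exudate are recorded as present or absent, and only vitreous cells, haze and hemorrhage are graded.

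The core change costs a few lines of SAP text and one derivation applied to both examinations, with no new data. The optional flag would need a rule for each finding.
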